Derby .04	[name] Or [name] Dept of Palliative Medicine, M&G Lvl 3, Royal Derby Hospital, [name]	[name]	
Guy's .05	[name] Guy's & St Thomas' NHS Foundation Trust, Guy's Hospital, [name]	[name]	[name]

Bournemouth .06	[name] Royal Bournemouth & Christchurch Hospitals NHS Foundation Trust, The Royal Bournemouth Hospital, [name]	[name]	[name]
		[name]	
Poole .10	[name] Poole Hospital NHS Foundation Trust, [name]	[name]	[name]
Wolverhampton .11	[name] New Cross Hospital [name]	[name]	[name]
Stockport .12	[name] Stepping Hill Hospital Dept of Surgery clo [name]	[name]	[name]

Clinical enquiries: To the Research Nurse at site, and in consultation with the local Principal Investigator when appropriate or necessary.

This trial will be conducted in compliance with the protocol, Good Clinical Practice (GCP) guidelines and regulatory requirements.

.....

[name] MD FRCS
Professor of Surgical Oncology
1st August 2013

Summary of Trial

Aim

The purpose of this multi-centre study is to test whether there is concordance between bioimpedance and perometer arm measurements and in particular, whether bioimpedance identifies patients who are developing lymphoedema at an earlier stage, before arm volume measurement by perometry shows significant increases in arm volume.

Trial Design:

Endpoints

Primary endpoint:-

- 1) Incidence of lymphoedema (>10% arm volume increase compared to contralateral arm) at 2 and 5 years after axillary node clearance (*assessed by perometer scanning*).

Secondary endpoints:-

- 1) Comparison of multi-frequency BEA with perometer measurement.
- 2) Prediction of lymphoedema by multi-frequency BEA at 24 months.
- 3) Quality of life in each group (T01 and FACT B+4).
- 4) Multivariate model assessment of factors predicting lymphoedema at 24 months.
- 5) Lymphoedema symptoms related to changes in arm volume and bioimpedance readings.

Trial Intervention

First cohort; patients consented before January 2015

1100 women undergoing axillary node clearance for breast cancer will be invited to take part in preoperative baseline and 1,3,6, 9, 12,18, 24 month and then annual monitoring of arm volume by perometry and multi-frequency bioimpedance measurement.

These 1100 initial recruits will have 3 monthly reviews with arm assessments by perometer and bioimpedance, lymphoedema questionnaire and FACT B4 QoL will be assessed at 6, 9, 12, 18 months and then 2 years; they will be assessed annually thereafter.

Second Cohort; patients consented after January 2015, on version 3 (or later) of the patient information leaflet

A further 300 patients will then be recruited; these women, who are also undergoing axillary node clearance for breast cancer, will be invited to take part in preoperative baseline, 1, 3, 6, and 9month monitoring of arm volume by perometry. At all of these timepoints, apart from one month, participants will be asked to complete a lymphoedema questionnaire. FACT B4 and EQ-5D QoL will be assessed at baseline only.

Sample Size

1100 women undergoing axillary node clearance for breast cancer will be invited to take part in the five year study. A further 300 patients will take part in the nine month study, which will commence recruitment from March 2015.

1.0 INTRODUCTION

1.1 Lymphoedema

Lymphoedema is a swelling of the arm (>10% arm volume increase) after surgery or radiotherapy to the axilla. Lymphoedema occurs when the lymphatic system is unable to keep up with the normal demands of tissue homeostasis, resulting in fluid accumulating in the interstitial spaces of subcutaneous tissue.¹²¹ It is a progressive condition and has the following components: excess protein in interstitial fluid, oedema, chronic inflammation and, if untreated, can lead to fibrotic, thickened skin and tissues.¹³¹ Lymphoedema after breast cancer treatment is affected by the extent of axillary surgery and the exposure of the axilla to radiotherapy.

Around 30% - 40% of women develop lymphoedema after axillary node clearance (ANC), 80-90% will develop this complication within two years and the remainder over a period of years post surgery. Lymphoedema still occurs after sentinel node biopsy or axillary sampling although the incidence is much less. However, 30-40% of the breast cancer patients will be node positive and require axillary clearance with its subsequent morbidity. Consequently the management of lymphoedema is an important cost item in the NHS annual budget. The cost of managing chronic arm lymphoedema has been calculated as £220/patient/year and at least £7m per annum to the NHS.

The affected arm is uncomfortable, unsightly and prone to episodes of superficial infection. Lymphoedema causes significant psycho-social morbidity and a poorer quality of life in breast cancer patients¹⁵⁶¹ and there is an extensive 'backlog' of patients that will require treatment for a considerable number of years. Lesser degrees of arm swelling (greater than 1cm) occurs in up to 40% of cases after surgery, often leading to reduced arm movement and having a major negative impact on quality of life after breast cancer surgery.¹¹⁹¹

1.2 Diagnosis and measurement

[figure not shown]
Diagnosis of lymphoedema is frequently based on clinical criteria alone. Some clinicians consider that lymphoedema exists once limb circumference at any given point is at least 1.5 cm larger than the same point on the unaffected side,¹⁷¹ whilst others have made a 2cm change their defining criterion.¹⁸¹ Limb swelling is generally determined by repeated measurement of arm circumference at 4cm intervals from wrist to the shoulder. The volume is then estimated with the use of a cylindrical model. There are inherent difficulties with this method of measurement: variability; and possible inaccuracies between observers and repeated measurements. Swelling may be limited to one particular area of the limb and excess fluid may move from one part of the limb to the other.¹⁹¹

True volume measurement has been seen as a solution to these problems and has been carried out by water displacement techniques, but these are considered to be too cumbersome and inconvenient for routine use¹⁹¹ and are not available in most breast or lymphoedema clinics.

Measurement of arm volume is performed in a reliable and operator-independent manner by use of a Perometer (Pero-System GmbH, Germany), a machine which calculates limb volume in cubic centimetres from optical measurements made by two sets of infra-red light sources directed at the limb at right angles^(11,121).

1.3 Quantification of Arm Swelling and Physical Functioning

Figure 1 ± Perometer

Reliable quantitative measures of therapeutic response are needed to monitor the effects of any therapeutic intervention on lymphoedema.

1.4 Perometer Measurement

Current methods of assessing arm volume include volume measurement using repeated tape measurement at predefined intervals along the limb, with the volume being calculated assuming a circular or elliptical truncated cone geometry. This method is tedious and time-consuming to perform. There is no standardisation of the number of circumferential measurements that are required to provide a reasonably accurate measurement of volume and it is thus not considered sufficiently validated to use in the study.

Perometry volume determined from the 3D silhouette cast by the limb when passed through a ray of opto-electronic sensors⁽¹³³⁾ is rapid, accurate and precise, but requires expensive equipment which is not very portable. The total volume of the arm may change for various reasons. The most common is weight gain but work or exercise induced muscle hypertrophy are cases in point where a simple total volume measurement is not immediately related to the parameter of interest i.e lymphatic volume. Additionally, there is dispute about the definition of lymphoedema. Many people have used the definition of greater than 10% arm volume increase compared to the contralateral arm, but others have claimed that a 200ml volume difference between the arms can be used to define unilateral lymphoedema following breast cancer treatment⁽¹⁴³⁾. For the purposes of this study, we are using a greater than 10% arm volume increase measured by perometer on at least two occasions to identify women with lymphoedema secondary to axillary node clearance.

The Perometer is a sensitive and standardised device that uses infrared optoelectronic technology to detect and quantify limb volume changes.^{11,26,27} Goltner et al reported that changes in interstitial tissue congestion up to 150ml may occur before limb swelling is visible and they quantified this volume change by using optometric perometry.²⁸³ They hypothesised that subclinical interstitial congestion is the basis for patient-reported sensory changes in the limb and is a precursor to the onset of lymphoedema.²⁹³

Arms will be measured on 2 occasions, 5-10 minutes apart using a Perometer. The average of the 2 measurements will be used to exclude intra-observer variability.

Cerniak et al found that perometer compared to bioimpedance spectrometry had a high concordance with bioimpedance $r=0.92$.

Physical functioning in this clinical context can be measured using a specific quality of life scale in upper limb lymphoedema, together with the FACT-B+4 Health Survey Questionnaire. Sentinel lymph node biopsy staging reduces the need for axillary node clearance (ANC), but 30% of breast cancer patients are node positive and require ANC to remove diseased nodes.^{116,17,191} A clinical endpoint of >10% increase in ipsilateral arm volume (versus contralateral arm) is an accepted criteria for a diagnosis of lymphoedema.^{8,20,21,22} Up to 40% of women develop lymphoedema by 18 months post ANC.¹⁹¹ Intervention before arm swelling becomes chronic may prevent the complications of lymphoedema after ANC.

In women undergoing axillary node clearance for node positive breast cancer in the ALMANAC Trial, 40% developed arm volume increases >10% (compared to baseline and contralateral arm) by 18 months post-surgery.

Arm measurements are not routine practice prior to axillary clearance but our data from an ongoing prospective study and the ALMANAC Trial¹⁹¹ data prospectively collected indicates that 40- 45% of patients develop arm volume increases between 4-8% by 3 or 6 months after surgery and 5% already have a 10% increase (i.e. Lymphoedema). The 45% of women with arm volume increases between 4-8% at 3 or 6 months post clearance account for the majority (50-60%) of patients who subsequently develop lymphoedema.²³¹ Counter-intuitively the absolute level of increase between 4 and 9% does not clearly define risk of later lymphoedema because despite no compression sleeve application up to 40% of women do not progress to develop lymphoedema by 2 years.

Conventional advice is that early arm swelling at 3 months does not portend chronic swelling and should be treated conservatively.²⁴ In the ALMANAC Trial¹⁹¹ prospective arm measurements identified early arm swelling (4-5%) in patients and predicted 53% of cases would subsequently develop lymphoedema (arm swelling 10%) by 18 months, whereas for 6% arm swelling, the specificity for subsequent lymphoedema was 80% (sensitivity 56%) and this degree of arm swelling at 3 or 6 months predicted 60% of lymphoedema cases at 18 months follow-up. Arm swelling of 4-8% is usually not clinically apparent unless arm measurements have been made preoperatively and only 3% of women in the axillary clearance arm of the ALMANAC Trial complained of significant swelling at 6 months^{19,251}

A recent prospective observational study identified women who developed 3% or greater arm volume increases after pre-surgery, baseline and 3 monthly measurements using a perometer. Forty three (out of 196) women then wore graduated compression garments for a mean duration of 4.4 (± 2.9) weeks, followed by continued use of the garments during strenuous exercise, or if swelling appeared. Arm reductions of 4.1% were observed ($p < 0.001$) which was maintained after an average follow up of 4.8 months.²⁹¹ Although the follow up and intervention period was limited, they argued for routine baseline measurement and early intervention with compression garments to prevent lymphoedema.

1.5 Multi-frequency Bioimpedance Electrical Analysis (BEA)

Multi-frequency bioimpedance electrical analysis (BEA) is a non-invasive technique to measure total water content, which involves passing an extremely small electrical current through the body and measuring the impedance (or resistance) to the flow of this current. In recent years the BEA technique has been refined to measure the impedance over a range of frequencies from 4 to 1000kHz. By mathematically modelling the measured data, the impedance at zero frequency (i.e. the impedance of the extracellular fluid alone) can be determined³¹¹. Multiple frequency BEA is used to compare quantitatively the degree of fluid accumulation in the arms using a leg as the reference limb and a 3sd change in BEA accurately diagnoses lymphoedema. Small single centre prospective studies in Australia have claimed that multiple BEA predicts lymphoedema development up to 10 months ahead of arm volume changes with a sensitivity of 98% and a specificity of 100%.³²¹ BEA can be measured with a handheld device and is marketed as safe,

accurate and diagnostic for lymphoedema (even in the absence of confirmed arm swelling >10%) to justify early treatment intervention in women after axillary surgery. BEA correlates with arm measurement but is reported to be more sensitive and equally specific as arm circumference measures particularly in women whose ANC involved the non-dominant arm lymphatics³³³.

On the basis of known disease progression, 90% of lymphoedema will have developed by 3 years after ANC surgery. At least 50% of breast cancer patients gain weight in the first year after diagnosis, and this is associated with increased risk of lymphoedema. Nonetheless, if careful contralateral arm measurements are not performed, weight gain, rather than true lymphoedema, can lead to inappropriate fitting of compression sleeves. Bioimpedance results (BEA) are unaltered by weight gain and we will test whether the bioimpedance results are similar to, more sensitive and/or more specific than, perometer measurements in detecting arm lymphoedema. Since bioimpedance is a non-invasive technique which can be measured with a mobile, hand-held device, if it is equivalent in sensitivity/specificity, it will be simpler to use in breast and lymphoedema clinics (for patients and clinicians alike), rather than a large, immobile, fixed perometer.

1.6 The Multi-frequency Bioimpedance in the Early Detection of Lymphoedema Trial

We will assess multi-frequency bioimpedance monitoring compared to perometer arm measurements in women after axillary node clearance (ANC) in 9 centres for the first 1100 patients enrolled in the 5 year study. We will use bioimpedance monitoring during the study to determine its value in predicting response to compression garment therapy. Within the study we will assess reproducibility of both methods across centres and robustly establish both intra and interobserver error rates for both methods in the study population. Subsequent recruits, as part of the 9 month study, will not undergo this as enough data will be gathered from the original cohort.

All women undergoing ANC in the UHSM Breast Unit have been invited to have preoperative 1,3,6,12 and 18 monthly bilateral arm measurements with a perometer (Pero-Systems 350S) and circumferential arm tape measurements. Of the last 270 women approached undergoing ANC within the last 11 months, 183 (67%) agreed to participate. We will use 9 centres who will monitor women undergoing ANC from pre-surgery baseline with perometer measurements and BEA to compare the sensitivity and specificity of both techniques for predicting chronic lymphoedema development. Identifying the most sensitive and specific method for detecting chronic lymphoedema would enhance selection of patients for intervention with arm sleeves should the intervention prove cost effective. Please note, this assessment will only be carried out in the initial 1100 recruits, as part of the 5 year study.

We have negotiated agreement with the manufacturers for provision and training in the use of L-DEX U400 bioimpedance spectroscopy devices for all centres taking part in the 5 year study with the appropriate software and electrodes to carry out a health technology assessment.

2.0 TRIAL DESIGN

1100 women undergoing ANC for breast cancer in 9 centres across the UK will be approached to undergo baseline (pre-operative) and subsequent BEA monitoring, along with perometer arm measurements (see flow diagram). A comparison of the sensitivity and specificity of BEA versus perometer measurement will be made firstly in women who develop arm swelling >10% by 6 months (estimated at 231/1100 (21%) of the initial group). Percentages are estimated from ALMANAC Trial (see Annex 4d). Secondly women with an arm volume increase 4-8.9% at 1, 3, 6 months where effectively the BEA 6 months readings will be compared with final 18 month perometer scores to assess the prediction of lymphoedema at 18 months by BEA. Thirdly, women with a <4% Perometer arm volume increase up to 6 months (estimated n=363/1100 with estimated lymphoedema at 18 months of 46 (14% of 264)) will be used to determine the sensitivity and

specificity of BEA 6 month measures compared to the perometer 6 month measurement in predicting the 18 month outcome.

We originally estimated we would need to screen over 1000 patients to enrol sufficient women into the PLACE Trial using perometer measurements, we will determine if BEA has a >80% sensitive and a >80% specific accuracy and currently the specificity of arm swelling measured by perometer is 87% specific for subsequent lymphoedema at 18 months with a sensitivity of 54% (assessed from ALMANAC trial data). We will recruit 1100 women before ANC into the five year study to allow for 10% drop-out over the course of the study.

The Perometer sensitivity is reported as 85% +/-3.6% (95% CI 81.4% to 88.6%) and we will be able to detect a greater or equal to 7% improvement in sensitivity with BEA to 92+/-2.5% (95%CI: 89.5-94.5%) and the Perometer specificity is 55% +1-4.1% (95% CI 50.9% to 59.1%) thus we will be able to detect a >9% improvement in specificity with BEA to 64%+/-3.9% (95%CI:60.1 to 67.9%) with this sample size, since the confidence intervals do not overlap.

Gold standard at 18 months	Test P+	Test P-	Total
	+168[contact]
	-168[contact]
Total	336[contact]

sensitivity = 307/352 = 87%
 specificity = 284/523 = 54%

Arm volume measurement at 1 month will not be used to implement treatment outside of the trial. In women who develop lymphoedema >10% at 3 months, sleeves will be applied and the 3 month BEA value compared to the perometer used in the analysis. For all others, the 6 month value will be used.

[figure not shown]
Please note, the BEA assessment will only be carried out on the initial 1100 recruits, as part of the 5 year study. Subsequent recruits, as part of the 9 month study, will not undergo this as enough data will be gathered from the original cohort.

Multivariate Model for Lymphoedema Development

Older age, increases in body mass index and postoperative radiotherapy are claimed to increase lymphoedema development^{8,363}. We will build a multivariate model predicting lymphoedema and will enter the following potential predictor variables: Body Mass Index, dominant limb, postoperative radiotherapy, previous sentinel node biopsy, cigarette smoking, weight gain and age. Follow up will allow us to identify what factors, as well as early arm volume changes or BEA, predict subsequent development of lymphoedema. We anticipate 1100 patients recruited by 24 months of the programme to allow us to build a multivariate model. Multiple logistic regression modelling techniques will be used to identify significant predictors of lymphoedema at early (18 months) and late time points (36 months).

An economic model will be developed, combining the economic data obtained from the planned lymphoedema prevention trial (PLACE Trial) with the multivariate prediction model to assess the cost-effectiveness of BEA in the context of either conventional management or proactive prevention of lymphoedema.

Figure 2 - BEA Trial Schema

Please note, the BEA assessment will only be carried out on the initial 1100 recruits, as part of the 5 year study. Subsequent recruits, as part of the 9 month, will not undergo this as enough data will be gathered from the original cohort.

**Five year study
(first 1100
patients)**

	Baseline	1 month post ANC	3 months post ANC	6 months post ANC	9 months post ANC	12 months post ANC	18 months post ANC	24 months post ANC	36 months post ANC	48 months post ANC	60 months post ANC
Informed Consent	X										
Height	X										
bioimpedance measurements *	X	X	X	X	X	X	X	X	X	X	X
Blood sample **											
Perometer measurements	X	X	X	X	X	X	X	X	X	X	X
Weight EQ-5D questionnaire	X			X	X	X	X	X			
FACT-B+4 questionnaire	X		X	X	X	X	X	X	X	X	X
lymphoedema symptom questionnaire	X		X	X	X	X	X	X	X	X	X

	Baseline	1 month post ANC	3 months post ANC	6 months post ANC	9 months post ANC
Informed Consent	X				
Height	X				
Perometer measurements	X	X	X	X	X
Weight EQ-5D questionnaire	X				
FACT-B+4 questionnaire	X				
lymphoedema symptom questionnaire	X	X	X	X	X
	X				
	X				
	X		X	X	X

NB. PaxGene sample does not appear on the schedule as it can be taken at any visit whilst the patient is on the study, as long as they have consented.

* use the form at the back of the protocol for guidance

** Patient needs to give additional informed consent on Consent Form B before these can be taken

NB. PaxGene sample does not appear on the schedule as it can be taken at any visit whilst the patient is on the study, as long as they have consented

Nine month study (final 300 patients, recruited from February 2015)

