3.4 Treatment Measurements

For the first 1100 recruits (recruited before January 2015), arm volume will be measured at baseline, 1, 3, 6, 9 and 12 months then 6 monthly thereafter to 2 years, followed by annual measurements to 5 years using perometer arm scanning (and circumferential tape measurement of arm girth with anatomic landmarks (e.g. lateral epicondyle) as reference points). The contralateral arm will act as a control. *For the additional 300 patients (recruited from February 2015, on version 3.1 or higher of the patient information leaflet), these measurements will take place at baseline, 1, 3, 6, and 9 months only.*

Patients developing a 4-8.9% increase in arm volume within 9 months of arm surgery will be offered randomisation. Within the same visit, patients will undergo multi-frequency bioimpedance measurements, comparing the affected arm with the contralateral arm and the leg. Bioimpedance measurements will not lead to change of treatment but will be recorded and performed according to the trial Standard Operating Procedures (please note, Bioimpedance will only be measured in

the 1100 patients who are part of the 5 year study. Subsequent patients, who will only be followed up for 9 months, will not undergo this assessment).

Perometer measurements demonstrating an increase in arm volume >10% (on two occasions) will be utilised to commence treatment for lymphoedema.

For the first 1100 participants, FACT B+4 questionnaires will be administered at all visits apart from the 1 month visit to permit calculation of Trial Outcome Index (FACT B TOD following the ATAC Trial methodology. ^[PG 60] A lymphoedema symptom questionnaire will be administered at the same time points. EQ5D questionnaires will be administered at all time points apart from months 3, 36, 48 and 60.

Please note, quality of life questionnaires will only be administered at baseline for the final 300 participants.

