All percentages for the 3 groups (A-C) are estimated from ALMANAC Trial data (see Annex 4d). None of the analyses outlined will use cases where a treatment for lymphoedema has been given prior to 6 months as explained above. A "treatment paradox" will not affect analyses 1 to 3 and treatment will be a variable in analysis. Potentially, the predictive value of a measurement at 6 months by perometry of the arm may be altered by treatment when assessing lymphoedema at 18 or 36 months. We do not believe this will occur for the majority of patients but in any case we will take account of this in the Cox multivariate regression analysis based on perometer measurements at 18 and 36 months and by looking at variables which include treatment with a compression sleeve. As we indicated in the flow diagram of this study, 3 possibilities may arise:

- Group A: Women in whom the arm volume increase is less than 4% at all time points up to 6 months (approximately 33% of the population; 330 individuals). None of these patients will undergo treatment within the first 6 months and therefore the measurement at 6 months will not be subject to "treatment paradox" and should they subsequently develop lymphoedema before 18 months, they will be registered as having developed the lymphoedema event in a time-dependant manner for the multivariate analysis and subsequent treatment will not affect this analysis.
- Group B: Women who will have developed a 4-10% arm volume increase by 6 months (estimated as 46% of the total group; 460 patients). Around 135 women from this group (with a 4-8.9% volume increase) will go into the PLACE trial and have a sleeve applied and a similar number will go into the PLACE trial and will not have an arm sleeve applied.

Thus, in this group there will be 325 patients (460 minus 135) who are not treated until they develop lymphoedema and will not have a "treatment paradox" for the same reason as previously described. Out of the 135 cases allocated to the sleeve arm within the PLACE trial, who are chosen at random, we will use their data in a multivariate analysis as we will incorporate it as a factor, sleeve versus no sleeve in building the model.

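### Women sleeved in PLACE from 6 months on stay in the Section 2.0 table of 6-month BEA against 18-month lymphoedema (4-8.9% group), so BEA specificity is biased downward if the sleeve works

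*Protocol*

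**What the plan says.** Protocol Section 2.0 sets out three comparisons. In the second, for women with a 4-8.9% increase at 1, 3 or 6 months, the plan is one "where effectively the BEA 6 months readings will be compared with final 18 month perometer scores to assess the prediction of lymphoedema at 18 months". In the third, for women below 4% up to 6 months, 6-month BEA and 6-month perometer readings are each judged against the 18-month outcome. The same section states the aim "we will determine if BEA has a >80% sensitive and a >80% specific accuracy".

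Section 3.4 says "Patients developing a 4-8.9% increase in arm volume within 9 months of arm surgery will be offered randomisation".

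Section 5 describes Group B (4-10% by 6 months) as "estimated as 46% of the total group; 460 patients" and adds "Around 135 women from this group (with a 4-8.9% volume increase) will go into the PLACE trial and have a sleeve applied". It then says "in this group there will be 325 patients (460 minus 135) who are not treated until they develop lymphoedema". Of Group A (below 4%) it says "None of these patients will undergo treatment within the first 6 months and therefore the measurement at 6 months will not be subject to" a treatment paradox.

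Section 5 concedes that treatment may alter the predictive value of a 6-month perometer measurement for later lymphoedema. It states two remedies: no outlined analysis uses cases treated before 6 months, and the Cox model (Analysis 4) carries a sleeve factor. Under Group C it says that all other patients, which includes sleeved Group B women, are eligible for the analysis predicting arm swelling at 18 and 36 months.

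**The concern.** The second comparison asks whether a 6-month BEA reading foretells lymphoedema a year later. Between reading and outcome, some of these women wear a sleeve meant to prevent that outcome. A woman whom BEA correctly flags, and whose lymphoedema the sleeve then prevents, is counted as a false positive. A sleeve factor in a Cox model cannot repair a two-by-two table, and the pre-6-month exclusion does not reach sleeves started at 6 or 9 months.

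Section 5's assurance that the treatment paradox spares Analyses 1 to 3 rests on paired readings: BEA and perometer status taken at the same time are affected together. That argument does not carry over to a reading at 6 months and an outcome at 18.

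The accuracy of BEA as a predictor feeds the economic model (Section 11) and the choice of method for selecting women for sleeves (Section 1.6). The bias appears only if sleeves work, which is when that choice matters most.

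**Working it through.** **The plan's own figures.** 460 − 135 = 325, as stated; 135/460 = 29%. The 18-month total of 350 is 35% of 1,000 (Analysis 2).

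**Inputs.**
- N = 460 (Group B). This includes women at 9-10%, so it slightly exceeds the 4-8.9% group.
- S = women sleeved at or after 6 months. The maximum is 135. The protocol does not split sleeve starts by date, so half (68) and a quarter (34) are shown as assumptions.
- p = untreated 18-month risk in Group B. Lower value: (350 − 210 − 46)/460 = 94/460 = 20%, using Group C's 210 and Group A's 46 events. Upper value: Section 1.4 says women with 4-8% swelling supply 50-60% of later cases, so 175-210 of 350, or 38-46% of 460.
- r = relative reduction from the sleeve. Not in the protocol; assumed 25% and 50%.
- True sensitivity (Se) and specificity (Sp) of BEA = 80% each, as a reference point.

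**Formula.** Prevented cases = S·p·r. If the sleeve effect does not depend on the BEA result, a share Se of them are BEA-positive (false positives) and 1 − Se are BEA-negative (true negatives):

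expected specificity = [N(1−p)·Sp + S·p·r·(1−Se)] / [N(1−p) + S·p·r]

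Example, S = 135, p = 0.20, r = 0.25: prevented = 6.75; (368 × 0.8 + 6.75 × 0.2)/374.75 = 295.75/374.75 = 78.9%.

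Example, S = 135, p = 0.46, r = 0.50: prevented = 31.05; (248.4 × 0.8 + 31.05 × 0.2)/279.45 = 204.93/279.45 = 73.3%.

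| Sleeved from 6 months | p=20%, r=25% | p=20%, r=50% | p=46%, r=25% | p=46%, r=50% |
|---|---|---|---|---|
| 135 | 78.9% | 77.9% | 76.5% | 73.3% |
| 68 | 79.5% | 78.9% | 78.2% | 76.4% |
| 34 | 79.7% | 79.5% | 79.1% | 78.2% |

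At r = 0 every cell is 80%. Under the same independence assumption sensitivity is not biased; it only rests on fewer events.

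**True specificity needed to read 80%.** Sp = 0.8 + 0.6·S·p·r/[N(1−p)]. With S = 135 this runs from 81.1% (p = 20%, r = 25%) to 0.8 + 0.6 × 31.05/248.4 = 87.5% (p = 46%, r = 50%). With S = 34 it runs from 80.3% to 81.9%.

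**Chance of reading above 80%.** For a test truly 82% specific, with p = 20% and S = 135, a binomial calculation gives 84% with no sleeve effect, 65% at r = 25% and 47% at r = 50%.

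**Group A.** The share first reaching 4-8.9% at 9 months is not given. Assume 10-20% of 330, PLACE uptake of 270/460 and half sleeved: 330 × 0.10 × 0.587/2 = 9.7, up to 19.4 women. At 20-46% risk and r = 50%, 1.0 to 4.5 of 46 events are lost. With 330 − 46 = 284 untreated negatives, specificity moves from 80% to 79.8-79.1%. At Group A's own 14% risk the loss is 0.7-1.4 events. (Section 2.0 gives "estimated lymphoedema at 18 months of 46 (14% of 264"; 14% of 264 is 37, whereas 14% of Section 5's 330 is 46.)

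**The case against.** Several points on the other side stand.

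- **The plan does more than the Cox adjustment.** Section 5 excludes cases treated before 6 months, and its Group B wording counts sleeved PLACE women as treated. A reader might infer that all 135 distort the table; 135 is only an upper bound. However, Analysis 1 accepts treated cases, so the protocol contradicts itself on who is excluded.
- **A true 80% does not satisfy a criterion of more than 80%.** Even without sleeves it would read above 80% only about half the time. One might conclude that the sleeve makes an 80% test fail; the supportable statement concerns tests truly above 80%.
- **The criterion is not tied to this subgroup.** Taken over 1,000 women with 650 negatives, the 20% risk case gives 79.4% (r = 25%) and 78.8% (r = 50%). Section 5 judges whether BEA can replace the perometer by same-time agreement, and the primary endpoint is perometer incidence; neither is touched.
- **A 60% risk is tempting but does not fit.** Section 1.4 says up to 40% do not progress, and 60% would give 69.2% at r = 50%. But it means 276 + 210 + 46 = 532 events against 350 planned. Even 46% is generous: 210 + 46 leaves 94 events for Group C's 210 women.
- **Group A is a minor matter.** The statement about the first 6 months is literally correct, and the 9-month inputs above are assumptions.

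The objection that the plan already recognises the problem does not succeed. It names the risk, then gives a remedy that does not reach this comparison. An SAP might supply one, but the protocol states both who is eligible and where the adjustment is made.

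**Conclusion.** The point holds for the 4-8.9% comparison. Women sleeved at or after 6 months stay in the table, and specificity is biased downward whenever the sleeve works and BEA discriminates better than chance (sensitivity above 1 − specificity). From a true 80%, the expected loss is about 1 to 7 percentage points if all 135 are sleeved from 6 months, 0.3 to 2 points if 34 are, and nil if the sleeve has no effect. These figures rest on an assumed 25-50% reduction, an untreated risk of 20-46%, and a sleeve effect that does not depend on the BEA result.

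The documents do not support a claim that both prediction comparisons are undermined, that BEA is bound to fail, or that the main conclusions of the study are at risk. This is a directional bias in a secondary analysis, worth removing because removal is cheap.

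**What to change.** In Section 2.0, state that the main 6-to-18-month sensitivity and specificity are estimated in women not allocated to a PLACE sleeve by 9 months, with the 6-month BEA reading kept as the index test. PLACE no-sleeve women may be weighted by the inverse of the actual allocation probability so that they stand for both arms; a weight of 2 is right only if allocation was 1:1. Show the all-women result and results by PLACE arm as sensitivity analyses.

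In Section 5, reconcile Analysis 1, which accepts treated cases, with the later statement that no analysis uses cases treated before 6 months. Say whether a PLACE sleeve counts as treatment for that rule. Qualify the Group A statement for PLACE entry at 9 months.

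The cost is wording, linkage to PLACE allocation, and precision. The 95% half-width at 80% specificity is 1.96·√(0.16/n). With all 460 women it is 4.1 points (368 negatives, p = 20%) to 5.0 (248, p = 46%). With 325 it is 4.9 (260) to 5.9 (175.5). With 1:1 weighting the effective size is 460²/(190 + 4 × 135) = 290, giving 5.1 to 6.3. At the less plausible 60% risk the unweighted figure is 6.9. The loss is therefore about one point, for an estimate that no longer depends on how well the sleeve works.
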